13. APPENDICES

Appendix 1. Study Procedures Table

	Visit 1: Screening (Day -1)	Visit 2: Baseline Assessments, Randomization, and Treatment Assessments (Day 1)	Visit 3 ^a : Day 3 (±24 hours)	Visit 4: Day 5 (±24 hours)	Visit 5: Day 7 (±24 hours)	Visit 6: Day 9 (±24 hours)	Visit 7: Day 13 (±24 hours)	Visit 8: Day 17 (±24 hours)	Visit 9: Day 22 (±24 hours)	Visit 10: End of study/ Day 28 (+3 days)	Optional Extended Viral Monitoring ^m			
											Visit 11: Day 35 (±48 hours)	Visit 12: Day 42 (±48 hours)	Visit 13: Day 49 (±48 hours)	Visit 14: Day 56 (±48 hours)
Must complete visit in the hospital or clinic	X	X	X ^j	X		X	X	X	X	X				
Written Informed Consent	X													
Medical History and Demographics	X													
Chest X-Ray	X ^a													
Screening Labs	X ^b													
Urine or Serum Pregnancy Test ^c	X	X		X		X	X	X						
FLU-PRO		X		X		X								
Vital Signs (inc. O ₂ Saturation ^d)	X	X	X ^o	X	X ^o	X	X	X	X	X				
Height	X													
Weight	X	X		X		X	X	X	X	X				
12-lead ECG		X						X		X				
Local Troponin Testing ^p		X						X		X				

	Visit 1: Screening (Day -1)	Visit 2: Baseline Assessments, Randomization, and Treatment Assessments (Day 1)	Visit 3 ^a : Day 3 (±24 hours)	Visit 4: Day 5 (±24 hours)	Visit 5: Day 7 (±24 hours)	Visit 6: Day 9 (±24 hours)	Visit 7: Day 13 (±24 hours)	Visit 8: Day 17 (±24 hours)	Visit 9: Day 22 (±24 hours)	Visit 10: End of study/ Day 28 (+3 days)	Optional Extended Viral Monitoring ^m			
											Visit 11: Day 35 (±48 hours)	Visit 12: Day 42 ±48 hours	Visit 13: Day 49 (±48 hours)	Visit 14: Day 56 (±48 hours)
Safety Labs ^e		X		X		X	X	X	X	X				
RSV antibody titer		X								X				
RSV Viremia		X		X		X	X	X	X	X				
Nasal Samples ^f	X ^r	X	X	X	X	X	X	X	X	X	X	X	X	X
Local RSV testing	X ^s								X ^l					
Randomization		X												
IMP Administration		X		X		X	X	X						
PK sample		X ^g	X ⁱ	X ^h		X ^h			X ^h					
Serum creatinine		X ^k				X ^k								
Adverse Events	X	X	X ⁿ	X	X ⁿ	X	X	X	X	X	X ⁿ	X ⁿ	X ⁿ	X ⁿ
Assess ICU admissions, hospitalizations, standard of care test results, mechanical ventilation, and supplemental O ₂		X	X ^o	X	X ^o	X	X	X	X	X				
Concomitant Medications	X	X	X ^o	X	X ^o	X	X	X	X	X				

- a Chest X-ray obtained < 48 hours prior to Screening may be used
- b Existing values collected ≤ 6 days prior to Screening may be used
- c Required for women unable to confirm menopause, hysterectomy and/or bilateral oophorectomy
- d On room air

- e Central laboratory testing: hematology and serum chemistry to include WBC with differential, Hgb, platelets, BUN, creatinine, serum albumin, AST, ALT, ALP, and TB
- f 2 samples total, 1 from each nostril – collected prior to dosing on dosing days
- g For subjects in the PK subgroup only: Collected 1 (± 15 min), 2 (± 15 min), 4 (± 30 min) and 6 hours (± 30 min) post-dose
- h For all subjects: collected pre-dose on Day 5, pre-dose and 2 hours (± 15 min) post-dose on Day 9, and anytime on Day 22
- i For subjects in the PK subgroup only: PK is collected anytime during Visit 3 and Visit 3 must occur in clinic.
- j For subjects in the PK subgroup only. Subjects not participating in the PK subgroup can have this visit completed at home by a home nursing vendor or by the study coordinator or designee.
- k For subjects in the PK subgroup only: Blood draw for serum creatinine 2 hours (± 15 min) post dose on Day 1 and Day 9 (Visit 2 and Visit 6)
- l Only for subjects who agree to the optional extended viral monitoring at the time of consent.
- m Only for subjects who agree to the optional extended viral monitoring at the time of consent and test positive (or inconclusive) for RSV at Visit 9 (Day 22)
- n Assessment of procedure-related AEs only, if home visit
- o Not required if home visit
- p Local troponin testing will be done pre-dose in accordance with the standard assay available and used at the site. Point-of-care “rapid” troponin tests are not acceptable for protocol-mandated troponin testing.
- q Visit 3: Day 3 is an optional study visit for subjects not participating in the PK subgroup.
- r For Japan sites only, 2 nasal swab samples will be obtained at Screening, 1 for local RSV testing and 1 for testing at the central laboratory. At Baseline, only 1 sample will be obtained for central lab testing.
- s Subjects who were not tested for RSV as standard of care may consent to the study and be tested for RSV during the Screening visit.

Appendix 2. Cardiac Adverse Events of Interest

The following search criteria are used to identify cardiac adverse events:

- All PTs from Cardiac disorders SOC
- Narrow scope PTs from the below SMQs, and associated sub-SMQs:
 - Cardiac arrhythmias (SMQ)
 - Cardiac failure (SMQ)
 - Cardiomyopathy (SMQ)
 - Ischaemic heart disease (SMQ)
 - Torsade de pointes/QT prolongation (SMQ)
- Select PTs from HLTs:
 - Cardiac histopathology procedures,
 - Skeletal and cardiac muscle analyses,
 - Arterial therapeutic procedures (excluding aortic),
 - ECG investigations, Cardiac function diagnostic procedures,
 - Heart rate and pulse investigations

Duplicate PTs were removed where necessary.

Appendix 3. Sample SAS Code for MMRM Model

The following model statement may be used for the analyses of viral load, FLU-PRO, O2 saturation, respiratory rate and EQ5D VAS scale as described in Sections 6.2.2 and 6.3.2:

```
proc mixed data=change;  
  class trt visit subjid strata;  
  model change = baseline strata trt visit trt*visit / s ddfm=kr;  
  repeated visit / type=un subject=subjid(trt);  
  lsmeans trt*visit / cl;  
run;
```

Note that since the response variable is change from baseline, the Visit 2 (baseline) value will always be 0 and should not be included in the above model.

An unstructured covariance will be assumed (type=un); if there are convergence or model fitting issues, then the alternative covariance structure of Toeplitz will be assumed (type=toep).

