1.3. Sample Size and Power

Sample size and power are estimated for the co-primary endpoints with the overall alpha level 0.05 (with alpha = 0.04 allocated to the development of a LRTC and alpha = 0.01 allocated to the time-weighted average change in viral load). The sample size calculations are based on the results observed in a study that evaluated the efficacy of oral and aerosolized ribavirin treatment for preventing progression from upper to lower respiratory tract infection in HCT recipients with RSV infections (unpublished data from [name]) and published data on currently used antiviral agents for RSV infections. {Shah 2013}

Assuming the time-weighted average change in RSV log₁₀ viral load from Day 1 to Day 9 in the placebo group will be -1 log₁₀ copies/mL, with a standard deviation (SD) of 2, 100 subjects per treatment group will provide over 80% power to detect at least 1 log₁₀ decrease in presatovir group using a 2-sided significance level of 0.01.

Assuming that 30% of subjects in placebo arm will develop a LRTC, 100 subjects per treatment group will provide over 90% power to detect at least 20% reduction in the proportion of LRTC in presatovir group with a 2-sided significance level of 0.04.

Using the fallback approach and the above assumptions for the co-primary endpoints, 100 subjects per arm will provide > 95% power to declare statistical significance in either change in viral load or proportion of subjects with LRTC.

Based on an administrative review of the data occurring in mid-September 2017, Gilead decided to halt the study on 20September2017 at an enrollment of 189 subjects despite the study not achieving complete enrollment of 200 subjects. The decision was made because enrollment of the remaining 11 subjects would have had minimal impact on study outcomes.

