3.6. Missing Data and Outliers

3.6.1. Missing Data

A missing data point for a given study visit may be due to any of the following reasons:

- A visit occurred in the window but data were not collected or were unusable
- A visit did not occur in the window
- A subject permanently discontinued from the study before reaching the window

Missing data can have an impact upon the interpretation of the trial data. As this study is of short duration, it is anticipated that missing data will be minimal. In general, values for missing data will not be imputed.

For laboratory data, a missing baseline value will be replaced with a screening value, if available; otherwise, it will be treated as normal (ie, Grade 0; no toxicity grade) for the summary of graded laboratory abnormalities. A retest value may be used if the first test is invalidated (eg, specimen hemolyzed).

Values will not be imputed for missing vital signs and other safety data. However, a missing baseline value will be replaced with the closest measurement prior to baseline, if available.

Missing viral load data due to premature discontinuation of the study will not be imputed as all available data will be included in the time-weighted average calculations. Intermediate missing viral load data will be imputed using the trapezoidal rule for the time-weighted average calculations, although only viral load data through Day 9 will be included in the primary endpoint calculations. As a sensitivity analysis, mixed-effects model with repeated measures (MMRM) for the absolute values and change from baseline in viral load will be applied. Similar analyses will be performed on FLU-PRO score and O₂ saturation.

All available data for subjects who do not complete the study will be included in the data listings.

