6.2.1. Time-Weighted Average Change in Nasal RSV Viral Load

The treatment difference in the time-weighted average change from Baseline (Day 1) to Day 9 in nasal RSV viral load (\log_{10} copies/mL) will be analyzed using a parametric ANCOVA with the baseline viral load (\log_{10} copies/mL) and stratification factors as covariates in the model. The test will be 2-sided with the significance level of 0.01. Nonparametric methods such as rank-based ANCOVA models or Wilcoxon rank sum tests may be implemented for exploratory purposes.

Adjusted means for each treatment group, 99% confidence interval (CI), and descriptive statistics (sample size, mean, SD, median, Q1, Q3, minimum, and maximum) will be presented in the descriptive summaries. Missing viral load data will be handled using the method described in Section 3.6.

6.2.2. Proportion of Subjects Who Develop a LRTC through Day 28

The proportion of subjects who develop a LRTC through Day 28 will be analyzed using a 2-sided Cochran-Mantel-Haenszel test stratified by the randomization stratification factors. The significance level used for the analysis (eg, 0.04 or 0.05) will be determined based upon the decision to reject the null hypothesis of the other co-primary endpoint as described in Section 3.5. The 2-sided 95% CI for the odds ratios between the 2 treatment groups will be constructed based on stratum-adjusted Mantel-Haenszel proportions.

The numbers and percentages of subjects who develop a LRTC through Day 28 will be provided with 95% CIs for the percentages based on the Clopper-Pearson method {Clopper 1934}.

The final analysis will be performed when all randomized subjects either complete Day 28 assessments or discontinue study prematurely.

The analyses of the co-primary endpoints will be repeated using the PP analysis set.

The primary efficacy analyses will also be repeated for the subgroups specified in Section 3.4, including the stratification factors (presence or absence of lymphopenia, treatment of RSV infection with ribavirin [yes or no] prior to randomization, sex, race, age group [< 65 or ≥ 65], type of transplant [autologous HCT or allogeneic HCT]. Adjusted mean and 95% CI will be presented by treatment group for exploratory purposes.

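### SAP Appendix 3: the planned unstructured MMRM is sound, but its only fallback forces one variance at every visit and its single baseline slope gives up some precision

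*SAP*

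**What the plan says.** SAP Section 3.6.1 gives the MMRM its role for viral load: "As a sensitivity analysis, mixed-effects model with repeated measures (MMRM) for the absolute values and change from baseline in viral load will be applied". The co-primary viral-load test is a different analysis. Under Section 6.2.1 the time-weighted average change (DAVG) "will be analyzed using a parametric ANCOVA with the baseline viral load" and the stratification factors, and "The test will be 2-sided with the significance level of 0.01".

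The MMRM itself is set out in Appendix 3. The mean model is "model change = baseline strata trt visit trt*visit / s ddfm=kr", so there is one baseline coefficient for all visits, with treatment and visit allowed to interact. On covariance, the appendix names its planned structure and the condition for leaving it: "An unstructured covariance will be assumed (type=un); if there are convergence or model fitting issues". Its remedy when that condition is met is a single alternative: "then the alternative covariance structure of Toeplitz will be assumed (type=toep". No heterogeneous-variance structure, empirical standard error or further step is named. The code requests treatment-by-visit means with confidence limits, so visit-level intervals are the output.

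The appendix is introduced permissively: "The following model statement may be used for the analyses of viral load, FLU-PRO, O2 saturation" and other scales.

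**The concern.** `type=toep` in PROC MIXED has one variance parameter and one correlation per lag. Every visit therefore gets the same residual variance, whatever the data show. Change from baseline in viral load is unlikely to have constant residual variance while some subjects clear the virus and others go on shedding. If the fallback were used, a visit-level interval could be too narrow or too wide purely because of the covariance structure.

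The single baseline slope is a separate and smaller matter. The dependence of change on baseline should be weak soon after Day 1 and strong once most subjects have cleared. A common slope fits neither end well.

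At stake is how well the named sensitivity analysis serves as a check on the viral-load result, together with any exploratory visit-level comparison that uses the same code.

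**Working it through.** **The plan's own figure.** The documents give no figure for the MMRM. The nearest is the DAVG power statement, "with a standard deviation (SD) of 2, 100 subjects per treatment group will provide over 80% power", for a 1 log10 difference at 2-sided alpha 0.01. Check: 1 / (2 × √(2/100)) = 3.54; 3.54 − 2.58 = 0.96; Φ(0.96) ≈ 0.83. The statement reproduces. It does not use the MMRM.

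**Inputs from the documents.** Nasal sampling after baseline is on Days 3, 5, 7, 9, 13, 17, 22 and 28, with Day 3 optional outside the PK subgroup (SAP 1.2 and Appendix 1). Enrolment stopped at 189 (SAP 1.3). Visit-specific SDs, correlations, baseline slopes and dropout are not given and are assumed below.

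**Parameter count, if all eight visits enter one model.** Unstructured: 8 × 9 / 2 = 36. Homogeneous Toeplitz: 1 + 7 = 8. Heterogeneous Toeplitz: 8 + 7 = 15.

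**Why slope and variance should change over time.** SAP 3.7.1 sets undetectable values to 0 and, where zeros occur, adds 1 before taking log10. A cleared subject then has log10(0 + 1) = 0, so change = −baseline: slope −1 with no residual scatter. Protocol 1.4 says most HCT patients shed for 15 days and some for as long as 21. Mid-course visits thus mix cleared and shedding subjects, and late visits have mostly cleared ones.

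**Closed form for the fallback, complete data.** Toeplitz SE / true SE at a visit = pooled SD / SD at that visit. For an SD rising linearly over eight visits from 1.5 to 2.5, pooled SD = √(2.0² + 0.107) = 2.03, where 0.107 is the variance of the eight SDs. The ratio is 2.03/1.5 = 1.35 at the first visit and 2.03/2.5 = 0.81 at the last. An SD of 1.8 to 2.2 gives 1.11 to 0.91; 1.0 to 2.5 gives 1.82 to 0.73.

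**Simulation of the Appendix 3 model.** 188 subjects, 300 replicates, strata omitted, 15% dropout, Day 3 missing in 60%. Entries are mean model SE / empirical SD of the visit treatment difference; Monte Carlo error is about 4%.

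| Assumed pattern | Unstructured, common slope | Toeplitz, common slope |
|---|---|---|
| SD 1.0 to 2.2, slope −0.15 to −0.90 | 0.93 at Day 3; 0.97–1.00 at Days 5–28 | 1.56 at Day 3; 1.14 at Day 9; 0.74 at Day 28 |
| SD constant, slope −0.15 to −0.90 | 0.94–1.02 | 0.94–1.05 |
| SD and slope constant, so only spacing is unequal | 0.99–1.02 at Days 5–28; 0.90 at Day 3 | 0.96–1.02 |
| Days 3 to 9 only, SD 1.2 to 1.8 | 0.95–1.05 | 1.20 at Day 3; 0.90 at Day 9 |

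In the first row, Toeplitz type I error at nominal 0.05 ran from 0.00 at Day 3 to 0.13 at Day 28. Adding `baseline*visit` while keeping Toeplitz did not cure this (1.61 to 0.76). Bias in the treatment difference was at most 0.03 log10 throughout.

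**With the SAP 3.7.1 floor built in.** Assumed: baseline mean 5–7 log10 with SD 1.5–1.8, lognormal clearance time with median 12–15 days, LLOQ about 2.5 log10. The baseline slope moved from between −0.10 and −0.16 at Day 3 to about −0.98 at Day 28. Pooled SD / visit SD was 1.22–1.43 at Day 3, 0.74–0.78 at Day 13 and 1.33–1.95 at Day 28. Another set of assumed clearance times put the low point at Days 7–9 (about 0.7) and Day 28 above 2. So the direction at each visit depends on the data.

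**Precision lost to the common slope (unstructured).** First row of the table, Day 28: empirical SD 0.384 with the common slope, 0.343 with visit-specific slopes; 1 − 0.343/0.384 = 11%. Day 9: 0.230 against 0.225, about 2%. Constant-SD pattern, Day 28: 0.269 against 0.249, about 7%.

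**The case against.** The strongest reply is that the planned model is the unstructured one and that it performs properly. Its standard errors were close to nominal even with the single slope kept, except at a sparse Day 3 (0.89–0.95), where visit-specific slopes did no better. That stands. A reader might infer from the code that the MMRM's error bars are wrong as planned. The documents do not support that: wrong standard errors need both a failed unstructured fit and unequal variances, and nothing shows how likely the first is.

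Nor is unequal visit spacing the cause. Spacing alone left the Toeplitz ratios at 0.96–1.02, and visits are evenly spaced at two days from Day 3 to Day 9. A general claim that late standard errors are too small also fails, because the floor can shrink the late variance and reverse the sign.

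FLU-PRO is collected after baseline only on Days 5 and 9. Its unstructured matrix has three parameters, so a forced fallback there is unlikely.

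The code is labelled as a sample, and SAP 6.4.2 is redacted, so the visits entering the model and further covariance detail may be stated there. This is a fair limit on the sizes above. It does not dispose of the point: Section 3.6.1 commits to the MMRM, and the sections Appendix 3 points to (6.2.2 and 6.3.2) describe Cochran-Mantel-Haenszel tests. In the visible text, Appendix 3 is the only specification of this model.

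**Conclusion.** The point holds as a low-cost improvement, not as a flaw in the planned analysis. If the fallback is reached and the residual variance differs by visit, which is likely for viral load given the floor and clearance during follow-up, visit-level standard errors will err in both directions across visits. For residual SDs rising from first to last visit, the closed form gives about 10% either way for a mild change (1.8 to 2.2) and 82% too large to 27% too small for a strong one (1.0 to 2.5). The single slope leaves the treatment difference unbiased and the unstructured standard errors essentially correct. It loses roughly 7% to 11% in SD at Day 28 under the assumed slopes, and little at Day 9.

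All these sizes rest on assumed variances, slopes, clearance times and missingness, and on all eight visits entering one model unless stated otherwise. It would be wrong to infer that the trial's main conclusions are exposed. The DAVG ANCOVA, the LRTC test, the secondary endpoint test and the sample size do not use this model.

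**What to change.** Make two edits to the Appendix 3 code and text.

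1. Add `baseline*visit` to the model statement. With eight visits this uses seven more fixed-effect degrees of freedom.
2. Replace `type=toep` with `type=toeph` as the first fallback. It has 15 covariance parameters against 36 for unstructured, and keeps visit-specific variances. If that also fails, use a simple structure with empirical (sandwich) standard errors; Kenward-Roger degrees of freedom must be dropped at that step.

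Both edits are needed to get the full benefit, since adding the interaction alone does not repair the Toeplitz standard errors. The cost is a few degrees of freedom and no change to data collection or to any alpha-controlled test. The gain cannot be fixed in advance, because it depends on quantities the documents do not give.

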Appendix 4. Sample SAS Code for Negative Binomial Model

The following model statement may be used for the analyses of number of hospitalization-free day, and supplemental oxygen-free day described in Sections 6.2.2 and 6.3.2:

```
proc genmod data=dataset;  
  class trt strata;  
  model count = trt strata / offset=logt dist=NB;  
run;
```

where logt is the offset parameter defined as the natural logarithm of study duration for each subject to account for potential differential study durations.

In the event that the negative binomial model fails to converge, a zero-inflated negative binomial model may be fit (dist=ZINB).
